### **Outcome Measures**

- Time to recovery (achievement of WH 80%, oedema-free), in days
- Rate of weight gain, in g/kg per day calculated from lowest weight to discharge weight
- Speed of loss of oedema, in days
- Failure to respond
- Morbidity, in number and duration of episodes over equal periods of follow-up for both groups
- Mortality
- Cost of treatment

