Upon resolution of acute illnesses including diarrhoea, pneumonia, gross electrolyte imbalance, or septicemia, severely malnourished children aged 6 months to 5 years will be randomized to receive any of the three treatment regimens:

1. Home-based nutritional rehabilitation with home follow-up (treatment A, n=75)
2. Home-based nutritional rehabilitation with outpatient follow-up (treatment B, n=75)
3. Hospital-based nutritional rehabilitation (treatment C, n=75).

Children on treatments A and B will stay in the NRU of the CRSC for a period of 7 days, during which their condition will stabilise and their mothers will have learnt the preparation of *khichuri* and *halwa*, which are low-cost, nutritious diets being successfully used in the CRSC. Following discharge after 7 days, these children will continue to be fed *khichuri* and *halwa* prepared by the mothers at home. Children on treatment A will be visited at home for follow-up by health workers at regular intervals during which growth will be monitored, micronutrients supplied, and morbidity recorded. This will continue until the children achieve an oedema-free weight-for-height (WH) >80%. Children on treatment B will be required to attend the outpatient follow-up clinic until they achieve oedema-free WH >80%. Children on treatment C will remain in the NRU and fed *khichuri* and *halwa* according to a standardized dietary schedule until achievement of a WH >80%. Outcome measures that will be used in comparing the three treatments will include growth, time to recovery (achievement of oedema-free WH >80%), rate of weight gain in g/kg per day calculated from lowest weight to discharge weight, speed of loss of oedema, failure to respond, morbidity (number and duration of episodes over equal periods of follow-up for both groups), mortality, and cost of treatment.

KEY PERSONNEL (List names of all investigators including PI and their respective specialties)

Name	Professional Discipline/Specialty	Role in the project
1. [name]	Paediatrician & Nutritionist	P.I.
2. [name]	Internist	Co-investigator
3. [name]	Paediatric Gastroenterologist & Nutritionist	Co-investigator
4. Medical Officer (to be named)	Physician	Co-investigator
5. [name] *	Nutritionist	Collaborating investigator

\* Reader in Community Nutrition  
London School of Hygiene & Tropical Medicine

Principal and co-investigators are from the Clinical Sciences Division, ICDDR,B.

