### **Treatment A**

In this treatment schedule, children will stay in the NRU for 7 days during which period their clinical condition will stabilise, and their mothers or caretakers will have learnt preparation of khichuri and halwa and taking care of the children at home. Thereafter, they will be discharged and health workers will visit them at their homes at regular intervals until they achieve a WH >80%, are free of oedema, and have a good general condition. If a child develops an acute illness or the general condition is not satisfactory at the time of discharge, then the discharge will be postponed till resolution of the illness. During stay in the NRU, calories and protein are gradually increased over a period of time in a programmed way in order to achieve rapid growth involving a weight gain of more than 10 g/kg per day. A major element of the method of nutritional rehabilitation practised in the NRU of the CRSC is that the diet given to the children contains proteins derived mainly from vegetable sources. Food containing animal protein such as milk (which is given only initially), eggs, meat or fish are expensive, and the mothers of these children can hardly afford these foods when continuing nutritional rehabilitation at home.

The diet schedule to be followed for the children is as shown on the following page. This is the standardized diet schedule that is currently being routinely practiced in the NRU of the CRSC.

Diet	Item & amount	Energy intake Kcal/kg.day	Protein intake g/kg.day
1	Milk suji 10 ml/kg.feed (110ml/kg.day) 2 hrly (11 feeds per day)*	74	1.5
	Halwa 10 g/kg.feed 2 feeds per day	48	1.0
	Total:	122	2.5
2	Milk suji 10 ml/kg.feed (110ml/kg.day) 2 hrly (11 feeds per day)*	74	1.5
	Halwa 10 g/kg.feed 2 feeds per day	48	1.0
	Khichuri 10 g/kg.feed 2 feeds per day	29	0.6
	Total:	151	3.1
3	Milk suji 100 10 ml/kg.feed (110ml/kg.day) 2 hrly (11 feeds per day)*	110	2.8
	Halwa 10 g/kg.feed 2 feeds per day	48	1.0
	Khichuri 10 g/kg.feed 2 feeds per day	29	0.6
	Total:	187	4.4
4	Milk suji 100 10 ml/kg.feed (110ml/kg.day) 2 hrly (11 feeds per day) *	110	2.8
	Halwa 10 g/kg.feed 3 feeds per day	72	1.5
	Khichuri 10 g/kg.feed 3 feeds per day	43	0.9
	Total:	225	5.2
5	Milk suji 100 10 ml/kg.feed (40ml/kg.day) 6 hrly (4 feeds per day)	40	1.0
	Halwa 20 g/kg.feed 3 feeds per day	144	3.0
	Khichuri 20 g/kg.feed 3 feeds per day	87	1.8
	Total:	271	5.8

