\* There is a gap in feeding at 4 a.m. Composition of milk suji and milk suji 100 (appendix 2)

Diets 1, 2, 3 and 4 will be provided on days 1, 2, 3 and 4 respectively. These diets ensure 2 hourly feeds with milk suji at least for the first 4-5 days of nutritional rehabilitation. Diet 5 is started when the child achieves an intake of 225 kcal/kg per day, which is possible by day 7. Most of the calorie and protein in diet 5 are derived from halwa and khichuri, the number of milk feeds being only four per day. The child will be given plain water in between the feeds, and breast feeding continued if applicable. The amount of each feed offered and actually taken will be recorded on a feeding chart. Upon discharge, the mother or caretaker will be advised to prepare khichuri and halwa at home and feed the child specified amounts or more for further nutritional rehabilitation. A plastic cup and a spoon will be provided to each child, but ingredients for khichuri and halwa will not be provided. A health worker will calculate the specified amounts of khichuri and halwa using a chart (appendix 3) and instruct the mother regarding the minimum number of cups of the diets to be given to the child each day.

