**Anti-helminthic treatment:** Children >1 year of age will be given mebendazole, 100 mg two times daily for 3 days, if such treatment has not been provided in the last six months. This treatment will be provided after two weeks of nutritional rehabilitation.

**Follow-up:** After the child is discharged from the NRU, a health worker will visit the child every week for one month and then at fortnightly intervals until the child achieves an oedema-free WH >80%. During each visit, the child's general condition will be assessed, weight and height (or length) measured, presence or absence of oedema noted, supplies of micronutrients provided, compliance of feeding and micronutrient supplementation checked by 24 hours recall, and morbidity recorded, if any. To aid recall of morbid conditions, on each visit mothers will be given a pictorial calendar portraying a well child and children with diarrhoea, vomiting, cough, fever, eye infection, or discharging ears [10]. Mothers will be requested to record daily on the calendar whether the condition had been present or absent in the previous 24 hours. Morbidity will then be recorded on a precoded form with the help of the calendar. Diarrhoea will be defined as the passage of three or more watery or liquid stools per day. An episode will be considered new if at least two diarrhoea-free days intervene between the present and previous episodes. The health worker's identification of children with pneumonia of different grades of severity will be based upon WHO guidelines [11]. Lack of weight gain for two consecutive visits will constitute failure to respond. The health worker will refer to the CRSC any child with suspected serious illness, i.e., diarrhoea with some or severe dehydration, pneumonia, ear or throat infection, repeated episodes of fever, loss of appetite, or failure to respond to feeding. Self referral will also be encouraged and entertained at any hour of the day. The child will be evaluated and managed accordingly by any of the investigators (during day time) or the on-duty physician (at night). Readmission to the hospital and the NRU will depend upon existing CRSC guidelines. Any child readmitted to the NRU will not be re-enrolled into the study, but will maintain the pre-readmission status as a study subject. The physician will also record in the precoded form diagnosis, treatment, duration, and outcome of any severe illness including relapse of severe malnutrition or septicemia.

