### **Treatment C**

Children on treatment C will remain admitted in the NRU until they have achieved an oedema-free WH >80%, and have a good general condition. This will typically involve a stay in the NRU for 15-25 days. The standardized feeding schedule will be followed and micronutrient supplements provided until discharge (refer to treatment A). Training of mothers or caretakers, immunization, and anti-helminthic therapy will be the same as in treatment A, except that in this treatment schedule the mothers or caretakers will receive more educational lessons due to their longer stay in the NRU. Morbid conditions occurring during rehabilitation, including diarrhoea, pneumonia, or septicemia will be recorded in precoded forms. After being discharged from the NRU, the children in this group will be advised to attend the NFU at intervals of two weeks for one month, and then at monthly intervals until they achieve a WH >90%. The entire family will be encouraged to come for the follow-up visit during which preparation of khichuri and halwa will be demonstrated to the mothers and then served to all members. Health education of the mothers or caretakers will be reinforced. Iron supplementation will be continued for 2 months in usual doses. Intercurrent illnesses such as diarrhoea or pneumonia will be treated.

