## Data Analysis

Describe plans for data analysis. Indicate whether data will be analyzed by the investigators themselves or by other professionals. Specify what statistical softwares packages will be used and if the study is blinded, when the code will be opened. For clinical trials, indicate if interim data analysis will be required to monitor further progress of the study. (TYPE WITHIN THE PROVIDED SPACE).

Data will be analyzed using the SPSS Windows software. The Epi Info software will be used to calculate anthropometric indices. Enrollment characteristics will be compared between the three treatment groups. The outcome variables will be compared both within and between groups from enrollment to discharge. For normally distributed quantitative variables, means will be compared by ANOVA. Variables not normally distributed will be log transformed before analysis. Categorical variables will be compared by Chi-square test, multiple or logistic regression will be performed to minimise bias if required.

Results from all randomized children will be included in the analysis of the study. Data from children withdrawn because of failure to respond, TB, or voluntary dropout will be included in the analysis upto the time of withdrawal. A supplementary analysis excluding the children withdrawn may also be made.

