## **Ethical Assurance for Protection of Human Rights**

Describe in the space provided the justifications for conducting this research in human subjects. If the study needs observations on sick individuals, provide sufficient reasons for using them. Indicate how subject's rights are protected and if there is any benefit or risk to each subject of the study.

This study will test the hypothesis that severely malnourished children recovering from diarrhoea, after an initial stabilisation period, can be rehabilitated nutritionally at home. As new drugs will not be tested, conduction of this study in human subjects is justified. After the acute phase treatment is over, the subjects in the study groups (home-based nutritional rehabilitation with follow-up at home or at the follow-up clinic) will be kept in the NRU for 7 days for stabilisation of general condition. Discharge from the NRU at the end of 7 days stay will be postponed if the general condition of a child is not stable. This will negate any risk to the subject.

After discharge at the end of 7-days stay in the NRU, the children will be visited at home or advised to attend the follow-up clinic at regular intervals. Any child failing to attend the follow-up clinic will be visited at his/her home. During the follow-ups at home or at the clinic, health and nutrition education will be reinforced, growth monitored, micronutrients provided, and the child referred to the CRSC if found to be ill.

The parents will always have the right to withdraw their children from the study at any time. Children withdrawn from the study will be provided with the conventional treatment at the CRSC. Mothers of children in the study group will not have to stay in the NRU for a prolonged period of time, which is an advantage for the families.

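### In arms A and B, discharge means leaving the NRU after the 7-day stay, so as written the weight-gain outcome and the comparison window stop before home care, contrary to the sample-size basis

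*Protocol*

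**What the plan says.** Outcome Measures lists "Rate of weight gain, in g/kg per day calculated from lowest weight to discharge weight". The Project Summary and the abstract for the Ethical Review Committee end the outcome at the same point. Data Analysis adds: "The outcome variables will be compared both within and between groups from enrollment to discharge".

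No section defines discharge for these purposes, but the word is used consistently for arms A and B:

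- Project Summary: "Following discharge after 7 days, these children will continue to be fed" the study diets at home.
- Treatment A: "Thereafter, they will be discharged and health workers will visit them at their homes at regular intervals until they achieve a WH >80" per cent; "Upon discharge, the mother or caretaker will be advised to prepare khichuri and halwa at home"; and, under follow-up, "After the child is discharged from the NRU, a health worker will visit the child every week for one month".
- Ethical Assurance: "After discharge at the end of 7-days stay in the NRU, the children will be visited at home" or seen at the clinic.
- Treatment B and the letter to the Ethical Review Committee about oedema use the word in the same way.

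For arm C it marks a different event: "Children on treatment C will remain admitted in the NRU until they have achieved an oedema-free WH >80" per cent and are in good general condition. The reply to the third external referee (point 10) also places C's NRU discharge at that target.

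**The concern.** One word ends the window for all three arms but marks two different events. In A and B it is the moment when home care starts. In C it is the end of rehabilitation. Diet, supplements and training in the NRU week follow the same schedule in every arm, and Clinical Economics itself puts the start of differential costs at 7 days after randomization.

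An analyst who follows the text would therefore compare a shared week in A and B with a full hospital course in C, on the outcome that sets the sample size. A second analyst, guessing that recovery was meant, would use different weights and could reach a different answer. The home-versus-hospital question would turn on which reading was chosen.

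**Working it through.** **1. The plan's own figure.** Inputs from Sample Size: hospital gain 8.4 g/kg per day, SD 7.3; home arm with outpatient follow-up 4 g/kg per day; power 90%; type I error 0.05 (taken as two-sided). The difference is 8.4 − 4 = 4.4. The protocol's formula gives

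n = 2 × 7.3² / 4.4² × (1.960 + 1.282)² = 106.58 / 19.36 × 10.507 = 57.8, so 58 per group.

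This matches the stated 58. Taking 4 as the difference would give 70, and a one-sided test 48, so 4 g/kg per day is the home arm's own rate. The other two stated requirements (15 and 24) are smaller, so weight gain drives the size. Allowing for dropout, 58 / 0.8 = 72.5, close to the stated 75.

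**2. Share of the home course left out.** The same section assumes about 35 days to WH above 80% in the home arm. With NRU discharge at day 7, 35 − 7 = 28 days follow it, and 28 / 35 = 80%. If discharge is postponed for illness, the extra days are still NRU care.

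**3. What each window can register.** Let g be the mean daily gain in the NRU week and h the mean daily gain at home. Use simple day-weighting, with the rate counted from the start of the NRU stay (a simplification, since the outcome starts at the lowest weight).

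- Window to recovery: (7g + 28h) / 35 = 0.2g + 0.8h.
- Window to NRU discharge: g.

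Home gain carries a weight of 0.8 in the first and zero in the second, whatever g is.

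**4. The literal contrast with arm C.** Take C's full-course rate as 8.4, as the protocol does. The literal difference is 8.4 − g. The protocol gives no first-week rate, so g is an assumption, shown over a range built from its own figures: 4 (the assumed home-arm rate), 8.4 (the full-course NRU rate) and 10 (Treatment A aims for more than this in the NRU). The home gain needed for an overall 4 g/kg per day is h = (4 × 35 − 7g) / 28.

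| Assumed g | Literal difference, 8.4 − g | h needed for an overall 4 | Difference to recovery |
|---|---|---|---|
| 4 | 4.4 | 4.0 | 4.4 |
| 8.4 | 0 | 2.9 | 4.4 |
| 10 | −1.6 | 2.5 | 4.4 |

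The planned 4.4 is stable only when the window runs to recovery. Read literally, the difference could vanish, change sign, or equal 4.4 without a single home day having been counted. The SD of a one-week rate is not given either, so no power can be stated for the literal contrast. For the intended contrast, power with 60 evaluable children per arm (75 × 0.8) is 91%.

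**The case against.** The best defence is that the intention can be recovered. The background describes the unit's routine discharge standard as WH above 80%, no oedema and good general condition. Treatment A uses the same three criteria to end home visits. The sample-size assumptions make sense only if measurement runs to recovery. That stands as evidence of intent. It does not repair the text: the routine meaning fits arm C only, every use of the word for A and B points to the NRU exit, and no section defines a later programme discharge.

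Nor is this a detail left to a statistical analysis plan. The protocol states an end point, and that end point conflicts with its own sizing.

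Three stronger readings are tempting, and the protocol does not support them.

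- *A reader might infer that deaths, illness and treatment failure at home are lost.* Time to recovery runs to the WH target. Morbidity is to cover equal follow-up periods and is collected at home. Costs start at day 7. Data Analysis includes all randomized children and keeps data up to withdrawal for failure to respond, which in A and B is judged at visits after NRU discharge. For these outcomes the stated window is a contradiction to remove, not proof of lost events.
- *A reader might infer that the 4.4 difference cannot appear under the literal rule.* It can. The diet is stepped up from 122 kcal/kg on day 1 to 225 on day 4, so a slower first week is plausible and could produce a spurious difference against C's full course.
- *A reader might infer that a known share of oedematous children would have no interval for a gain rate, because oedema takes a median of 7 days to clear.* That needs an undocumented link between lowest weight and loss of oedema. It also takes the one-third share among hospital admissions as the share in the trial, although enrolment of these children was still under discussion with the ethics committee.

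**Conclusion.** The point holds for the weight-gain outcome and for the comparison window in Data Analysis. As written, A and B are measured over the shared NRU stay and C over its whole rehabilitation, which contradicts the basis of the 58 per group. On the protocol's 35-day home course, 80% of the days lie outside the literal window, and home gain has no weight in the A and B result.

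The 80% rests on the protocol's own 35-day assumption and on discharge at day 7. The zero weight needs neither. The size and direction of the resulting error cannot be stated, because the first-week gain is not given. The sample size needs no change once the window ends at recovery. The wording should be settled before any analysis, because two readers of the current text could report different results for the outcome that drives the trial's size.

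**What to change.** 1. In the Project Summary, Outcome Measures and the abstract for the Ethical Review Committee, replace the end point of the weight-gain rate, for all three arms, with: *weight at first oedema-free WH above 80% or, if this is not reached, the last study weight before withdrawal, death or loss to follow-up*.
2. In Data Analysis, replace the comparison window with: *from enrolment to first oedema-free WH above 80% (or withdrawal, death or loss) for growth outcomes, and over the same fixed period from randomization in all arms for morbidity and mortality*. State that events after NRU discharge count in A and B.
3. Keep the word *discharge* for leaving the NRU. The clinical discharge rules are not affected.

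Running the window to the end of each child's follow-up would not serve. Clinic attendance towards WH above 90% is monthly in A but two-weekly and then monthly in C, so the windows would be unequal, although Outcome Measures asks for equal periods for morbidity.

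Cost: wording and minor analysis work. The weights for A and B are already taken at the planned home or clinic visits. The fixed period should lie within the planned follow-up of all arms. If it extends past C's NRU stay, the text should say that illness is recorded at C's clinic visits, since it now mentions recording for C only during rehabilitation.

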## Interventions

Upon resolution of the acute illness, eligible children will be randomized to receive any of the three following interventions:

1. Home-based nutritional rehabilitation with home follow-up (treatment A, n=75)
2. Home-based nutritional rehabilitation with outpatient follow-up (treatment B, n=75)
3. Hospital-based nutritional rehabilitation (treatment C, n=75).

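### Morbidity is promised over equal follow-up, but no common window is set, and recording stops at each child's own recovery, which is expected later in home-based than in hospital care

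*Protocol*

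**What the plan says.** Outcome Measures lists "Morbidity, in number and duration of episodes over equal periods of follow-up for both groups". The Project Summary and the abstract for the Ethical Review Committee repeat the equal-period wording. None of them gives a length or a start and end point. The wording implies two groups, while Interventions states that "eligible children will be randomized to receive any of the three following interventions".

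Observation is described arm by arm:

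- **A:** after discharge from the nutritional rehabilitation unit (NRU) at about day 7, visits take place "every week for one month and then at fortnightly intervals until the child achieves an oedema-free WH >80" per cent. For morbidity, "on each visit mothers will be given a pictorial calendar portraying a well child and children with diarrhoea" and other common complaints; mothers mark it daily, and "Morbidity will then be recorded on a precoded form with the help of the calendar".
- **B:** the same schedule and follow-up protocol as A, but at the nutritional follow-up clinic (NFU), with a home visit if the child does not attend within 2 days.
- **C:** "Morbid conditions occurring during rehabilitation, including diarrhoea, pneumonia, or septicemia will be recorded in precoded forms". Rehabilitation in the NRU typically lasts 15-25 days. After that, "the children in this group will be advised to attend the NFU at intervals of two weeks for one month", then monthly until weight-for-height exceeds 90%. No calendar, and no morbidity recording at these later visits, is stated.

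Data Analysis compares outcomes from enrolment to discharge and adds: "Variables not normally distributed will be log transformed before analysis". Mortality is listed as an outcome without a time window.

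**The concern.** Recovery ends the recording of illness, and time to recovery is itself an outcome that the protocol expects to differ between arms. The slower arm is watched for longer and can show more episodes and more deaths for that reason alone. The recording method also changes between A/B and C, and the weeks after C's discharge have no stated morbidity record, although A and B are recorded at home.

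The first hypothesis is that these children can be managed at home after a short stay. The Ethical Review Committee asked about the risk of sending oedematous children home, and the reply relied partly on equal mortality in an earlier Dhaka study. Morbidity and mortality are this trial's own evidence on that question. Data not collected after discharge cannot be recovered in the analysis.

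**Working it through.** **Inputs.** Sample Size gives 22.5 days (SD 6.2) to reach 80% in hospital, about 35 days in home-based care with outpatient follow-up, and 75 children per group. Treatment C gives a 15-25 day stay; Treatments A and B give 7 days. The reply to the Ethical Review Committee cites 3.5% mortality. The protocol gives no illness rate, so 0.25 to 2 episodes per child per 30 days is assumed here. Both recovery times are taken to run from randomization. No time is given for A, so the figures below compare B with C.

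**The plan's own figure.** The protocol gives none for morbidity. Its 58 per group for weight gain is reproduced: 2 × 7.3² / 4.4² × 10.5 = 57.8, that is 58. Then 58 / 0.8 = 72.5, that is 73, within two of the stated 75.

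**Length of observation if it ends at recovery.**

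- From randomization: 35 / 22.5 = 1.56. Against the stated NRU stay: 35 / 25 = 1.40 to 35 / 15 = 2.33.
- After the first 7 days, spent in the NRU by all arms: (35 − 7) / (22.5 − 7) = 28 / 15.5 = 1.81.

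**Length if the Data Analysis window means NRU discharge.** A and B have about 7 days and C has 15-25, so C is observed 15 / 7 = 2.1 to 25 / 7 = 3.6 times as long. The imbalance reverses.

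**Raw counts at identical true rates.** With rate r per 30 days, the expected episodes per child are m_C = r × 22.5/30 and m_B = r × 35/30. For Poisson counts and n = 75, d = (m_B − m_C) / √[(m_B + m_C)/n], and the chance that a two-sided 5% test declares a difference is Φ(d − 1.96) + Φ(−d − 1.96).

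| r | C | B | Declared different | No episode, C / B |
|---|---|---|---|---|
| 0.25 | 0.19 | 0.29 | 26% | 83% / 75% |
| 0.5 | 0.38 | 0.58 | 45% | 69% / 56% |
| 1 | 0.75 | 1.17 | 74% | 47% / 31% |
| 2 | 1.50 | 2.33 | 96% | 22% / 10% |

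For r = 1, d = 0.417 / √(1.917/75) = 2.61. With 58 per arm the four chances are 21%, 37%, 63% and 90%. The last column is exp(−m); for those children the log of the count is undefined.

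**Deaths.** A constant hazard giving 3.5% over 22.5 days gives 1 − 0.965^(35/22.5) = 5.4% over 35 days, with no true difference.

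**Method.** A and B share the calendar, form and schedule; only the place of contact differs. The contrast in method is therefore A and B against C.

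**The case against.** The strongest reply is that the equal-period wording already rules out raw counts over unequal time, and that truncation or person-time can be left to an analysis plan that is not shown. Part of this stands: the figures above show what happens if the arm-by-arm instructions are followed and nothing more is done, and they are not a forecast. But an analysis plan cannot supply calendar data that the protocol never schedules for C. Rates up to each child's own recovery would still compare ward time with home time, over a period fixed by another outcome.

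Several stronger readings are tempting, and the documents do not support them:

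- *C is unobserved after discharge.* NFU visits are scheduled and intercurrent illness is treated. What is missing is stated morbidity recording at those visits.
- *C will be lost because follow-up is known to be sub-optimal.* The Background says this of children who could not be accommodated in the NRU or who refused a long stay, not of children who completed it.
- *C's list of illnesses is shorter.* The list is introduced as examples and is not closed.
- *The home arm will show about 80% more episodes.* The 1.81 applies only to raw counts after day 7; from enrolment it is 1.56, and for B.
- *Mortality is recorded differently by arm.* The equal-period wording covers morbidity only, and recording method matters little for deaths. The mortality point is only that no common window is stated.

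The frequency of zero counts depends on the assumed rate, so the log-transformation issue is secondary.

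**Conclusion.** The concern holds in this form. Equal periods are promised, none is set, and the instructions for each arm produce unequal periods tied to recovery: 1.56 to 1 for B against C from randomization on the protocol's own expectations. The Data Analysis window does not settle the matter, because discharge falls at different times by arm, and the sections must be reconciled. The difference in recording between A/B and C would remain even with equal lengths.

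The 26% to 96% range rests on assumed rates, Poisson counts, a constant rate and no adjustment for time. Extra variation between children would lower it. A reader might infer that morbidity and mortality cannot be compared at all. That goes too far, since a common window and common recording would repair most of the fault. Morbidity is one of seven listed outcomes and does not drive the sample size. Severity: should-fix, before enrolment.

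**What to change.** 1. In Outcome Measures and Data Analysis, set one window from randomization for morbidity and vital status in all three arms, continued past recovery in each. Choose its end so that C's existing visits can supply the data. For stays of 15-25 days the two-week visit falls on days 29-39 and the one-month visit (28 days) on days 43-53. An end at day 42, for example, would be read from the calendar at the one-month visit. An end near day 37 would also rely on that visit for many children: at the mean stay the two-week visit falls on day 36.5, and a month of 30 days puts the next near day 52.
2. Use the same calendar and precoded form in C, in the NRU and after discharge, and in A and B during their NRU week.
3. Analyse episodes as rates, by Poisson or negative binomial regression with days observed as offset, in place of log-transformed counts.
4. Refer to the three groups wherever the outcome is defined.

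No treatment changes. The cost is calendars for C and for A and B children who recover before the window closes, plus some extra contacts. These must be costed: the 960 budgeted visits exceed A's 75 × 8 = 600, but Budget Justifications says that the transport also covers non-attenders in the clinic group, so the other 360 are not shown to be free. At 3,000 / 960 = $3.13 transport per visit, one extra contact for each of 75 children is about $234. For all 225 it is about $703, against direct costs of $74,124.
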